5.6.1 Procedural Details

The EndoRotor® will be set-up and used to resect the mucosa and submucosa to remove all gross visible disease. If the lesion is circumferential, the endoscopist shall resect no greater than 270 degrees of the radial circumference of the esophagus to avoid stricture formation. The resection is taken down to the muscularis propria layer to ensure all of the mucosa and submucosa is removed in the area of persistence.

Details of the subject's index procedure will be documented in the subject's source medical record and on the appropriate CRF, including:

- Date of Procedure
- Preoperative Diagnosis
- Method and Type of Sedation
- Concomitant Procedures Performed
- Verification of resection results

- Time of endoscope insertion and beginning of EndoRotor use
- Time the Procedure was Completed (end of EndoRotor use and time endoscope removed)
- Estimated Blood Loss
- Postoperative Diagnosis
- Lot and Serial Number of the EndoRotor® console and catheter
- Any Adverse Events

5.6.2 Post-Procedure Evaluations

Subjects will be discharged from the hospital upon satisfactory completion of all post-procedure recovery requirements as defined by the investigational site's standard protocol.

Post-procedure pain and dysphagia will be recorded for all subjects after each intervention.

Adverse events will be recorded in the subject's source medical record and on the appropriate CRF as they are observed.

5.7 Subject Follow-Up

If at any point during post-procedure subject follow-up, a subject's clinical presentation jeopardizes the safety or welfare of the subject, the Investigator should act in the best interests of the subject, utilizing any and all means judged medically necessary.

All endoscopic assessments will be saved in digital format. All files will be de-identified to maintain subject's confidentiality and submitted to the Sponsor along with the CRFs for data analysis.

5.7.1 Possible Follow-Up Scenarios

There are several scenarios with respect to each individual subject's timeline, regardless of which arm they are in.

5.7.1.1 Scenario 1 – Complete Response with negative biopsies on 2 consecutive surveillance endoscopies. The subject undergoes a treatment and returns in 3 months for surveillance. The biopsies are negative. The subject returns for his/her second surveillance endoscopy in 3 months and is found to have negative biopsies again. The subject is considered a complete responder and is taken out of the study. Time in the study is 6 months after the initial treatment, or about 7 months after recruitment.

5.7.1.2 Scenario 2 – Failure to clear disease with a positive biopsy after a second treatment with the EndoRotor® or continued ablative therapy. The subject undergoes a treatment and returns in 3 months for surveillance. The biopsies are positive. The treatment is performed again depending on which arm he/she is in (EndoRotor® or continued ablative therapy). The subject returns for his/her surveillance endoscopy in 3 months after the repeat treatment and is found to have positive biopsies again. The subject is considered a failure to respond and is taken out of the study. Time in the study is 6 months after the initial treatment, or about 7 months after recruitment.

5.7.1.3 Scenario 3 – Complete Response despite one positive biopsy. The subject undergoes a treatment and returns in 3 months for surveillance. The biopsies are positive. The treatment is performed again depending on which arm he/she is in (EndoRotor® or continued ablative therapy). The subject returns for his/her surveillance endoscopy in 3 months after the repeat treatment and is found to have negative biopsies. The subject returns for his/her surveillance endoscopy in 3 months and is found to again have negative biopsies and is considered a complete responder

and is taken out of the study. Time in the study is 9 months after the initial treatment, or about 10 months after recruitment.

5.7.1.4 Scenario 4 – Failure to clear disease despite one negative biopsy. The subject undergoes a treatment and returns in 3 months for surveillance. The biopsies are negative. The subject returns for his/her second surveillance endoscopy in 3 months and is found to have positive biopsies. The treatment is performed again depending on which arm he/she is in (EndoRotor® or continued ablative therapy). The subject returns for his/her surveillance endoscopy in 3 months after the repeat treatment and is found to have negative biopsies. The subject returns for his/her surveillance endoscopy in 3 months and is found to have positive biopsies and is called a failure to respond and is taken out of the study. Time in the study is 12 months after the initial treatment, or about 13 months after recruitment.

5.7.3 Follow-up Visit 6-Months (± 14 days)

The subject will return to the outpatient clinic for the 6-month visit. In the EndoRotor® arm, the EndoRotor® will be set-up and used to resect the mucosa and submucosa to remove all gross visible lesions. If the lesion is circumferential, the endoscopist shall resect no greater than 270 degrees of the radial circumference of the esophagus to avoid stricture formation. The resection is taken down to the muscularis propria layer. Results of the following study procedures will be recorded in the subject's source medical record and on the appropriate CRF:

- Surveillance endoscopy
- Resection or ablation with the EndoRotor or continued ablative therapy device, respectively, if lesions are present
- Adverse events
- Biopsy
 - Record biopsy results
 - Record the reduction in the number of activated fibroblasts in the submucosa of the healed resection areas

Should the endoscopy demonstrate complete absence of Barrett's esophagus at this visit (and they were negative at the 3-month surveillance), the subject will not need to return for the 9-month visit and will exit the study.

5.7.5 Unscheduled Visits

The subject may return to the outpatient clinic or phone the physician for any reason in their judgment, or in the judgment and upon request of the Investigator. Should such visit(s) occur, the Investigator will record all unscheduled visit findings, phone calls, endoscopy and laboratory results in the subject's source medical record and on the appropriate CRF.

5.8 Laboratory Testing Procedures

5.8.1 Specimen Preparation (EndoRotor® Arm Only)

The EndoRotor® specimen trap has a 1 micron filter that can be replaced once the lesion is fully removed. The trap is opened and the filter is removed and placed into a small jar with 10% formalin and then is sent to Pathology for histologic evaluation. Samples will be labeled in a blinded manner before being sent to pathology; however, it should be noted that ablative therapies do not allow for retrieval of pathology. Therefore, only the EndoRotor will include pathology from actual procedure.

Surveillance endoscopy biopsies will be obtained using standard endo-forceps and will be sent to Pathology in small jars of 10% formalin. Using the Prague Criteria to assess lesions that were previously treated the lesion can be biopsied using the Seattle Protocol which requires 4 quadrant biopsies per 1cm of length in the involved segment according to the standard of care for follow-up endoscopy. In the case of patients receiving EndoRotor treatments the patients are only receiving treatment on up to 270 degrees of surface area to avoid risk of stricture. Therefore, only positive biopsies in the EndoRotor® treated segment will be considered for further ablation. If biopsies in the EndoRotor treated section are negative they will continue with the follow-up endoscopy of the protocol until a second negative endoscopy according to the follow-up protocol. In a subset of the first 5 subjects (n=5), abnormal submucosal glands and fibroblasts will be harvested to determine the activity of cancer-associated fibroblasts in the submucosa before and after use of the EndoRotor® device. Dysplasia associated fibroblasts will be identified by their association with irregular shaped glands by Volume Laser Endomicroscopy. The areas will be marked using the laser marking device available on the VLE device.

After marking the areas with the system using two marks approximately a centimeter apart, the targeted area will be biopsied twice using a "keyhole" technique. This will ensure acquisition of the appropriate submucosal tissue.

5.8.2 Specimen Handling and Storage

Patient biopsy samples will be labeled per standard operating procedures of the site. The specimens are to be stored in Pathology and are subject to the rules and handling/storage/release of information regulations within the Department of Pathology.

Biopsy specimens will be processed and sections stained for the presence of dysplasia associated fibroblasts. These will be characterized by immunohistochemistry being positive for α -SMA and vimentin while negative for desmin and pan-cytokeratin.

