4.3 Primary Endpoints

4.3.1 Primary Effectiveness Endpoint

Complete removal of areas of Barrett's metaplasia after no more than two treatments.

The primary effectiveness endpoint will be measured by post-treatment visual appearance on surveillance endoscopies and the findings on histology from biopsies taken of the treatment site at each endoscopy.

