5.6 Follow-Up Procedures and Therapy Transitions

Surveillance endoscopy is performed in 3 months where there is visual inspection of the treated areas. Biopsies are taken from the areas treated with the respective device are sent to pathology to evaluate for the presence of intestinal metaplasia (Barrett's). If the samples are read as negative by Pathology (no Barrett's seen), the patient then undergoes another endoscopy in 3 months. If the results again are negative, the patient is declared to have a complete response to the treatment (EndoRotor® or ablative therapy).

If there is intestinal metaplasia (Barrett's) confirmed by the biopsy, the patient undergoes a second treatment with either the EndoRotor® or ablative therapy as described in Section 5.7. Two consecutive negative results at 3 month intervals between biopsies is required to consider these subjects complete responders.

If there is intestinal metaplasia (Barrett's) seen either at 90 days or at 180 days after either (EndoRotor® or cryotherapy / ablative therapy) second treatment, the patient is considered to have failed and will exit the study.

To evaluate the secondary endpoint of this study, "Percent reduction of the area with Barrett's esophagus that was resected or ablated during the initial treatment session through the final follow-up visits", percent reduction of the area with Barrett's esophagus will be determined by a decrease in overall length. Using the Prague criteria, both the circumference and maximal length of the Barrett's segment will be estimated. A percentage reduction in the length will be calculated by length measured at the follow up endoscopy divided by the total prior length.

Adverse events, as defined in Section 10.4, will be recorded from the index procedure (Day 0) through study completion and/or exit/withdrawal.

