5.8.3 Specimen Analysis

The resident pathologist shall be responsible for the review and interpretation of specimens collected.

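### Nothing in the plan secures masked reading of the surveillance biopsies that help decide the primary endpoint, so the reader may know the arm.

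*Combined protocol and SAP*

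**What the plan says.** Section 4.3.1 measures the primary effectiveness endpoint by visual appearance at surveillance endoscopy together with "the findings on histology from biopsies taken of the treatment site at each endoscopy". Section 5.6 makes the pathology result operative: "If the samples are read as negative by Pathology (no Barrett's seen), the patient then undergoes another endoscopy in 3 months". A second negative endoscopy gives a complete response. A biopsy showing metaplasia leads to a second treatment or, after that treatment, to failure and exit.

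Three subsections govern the specimens.

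- Section 5.8.1, whose heading limits it to the EndoRotor arm, opens with the resection filter. That paragraph contains the plan's only statement on blinding of specimens: "Samples will be labeled in a blinded manner before being sent to pathology". It goes on to say that ablation yields no tissue, and concludes: "Therefore, only the EndoRotor will include pathology from actual procedure". The next paragraph turns to the surveillance biopsies: "Surveillance endoscopy biopsies will be obtained using standard endo-forceps and will be sent to Pathology in small jars of 10% formalin". It does not mention blinding.
- Section 5.8.2 says: "Patient biopsy samples will be labeled per standard operating procedures of the site".
- Section 5.8.3 says: "The resident pathologist shall be responsible for the review and interpretation of specimens collected".

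**The concern.** Treatment cannot be masked from the endoscopist, because the devices differ visibly. Histology is the part of the endpoint that can be masked cheaply, and the plan does not clearly do so. A site could follow the protocol exactly and still send endpoint biopsies to a reader who can learn the arm from the label, the requisition or the patient's earlier specimens.

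If knowledge of the arm influenced readings in one direction, the responder proportions would be biased. Both confirmatory tests, non-inferiority and then superiority, use those proportions. Neither the covariate adjustment in section 7.4 nor the missing-data sensitivity analyses in section 7.5 would detect or correct such a bias.

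**Working it through.** **Step 1: which specimens does the blinding sentence cover?** Two readings are possible.

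- Narrow: the sentence stands in the filter paragraph, under an EndoRotor-only heading, so it covers filter specimens. The endpoint biopsies then have no masking rule. Blinded labels on filters would also hide little, since only one arm produces them.
- Broad: the sentence covers every sample in both arms. Section 5.8.2 then does not carry it through, because it sends biopsies out under site procedures with no reference to blinding.

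Neither reading secures masking of the endpoint histology.

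**Step 2: does another section close the gap?** Sections 6.2 and 10.2 give the independent committee adverse events to adjudicate, not histology. Section 9.7 mentions core laboratories only for record retention. No section describes a masked, central or second read.

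**Step 3: the plan's own figure.** Section 7.3 gives 91.6% superiority power for 80% versus 50% with 55 per arm. With pooled variance under the null and two-sided α of 0.05:

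z = [0.30 − 1.96·√(2·0.65·0.35/55)] / √(0.80·0.20/55 + 0.50·0.50/55) = (0.30 − 1.96·0.0910)/0.0863 = 1.41, so power = 92.1%.

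This agrees with 91.6% to within about half a point. The present point disputes no power figure; the check only confirms the setting for Step 4.

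**Step 4: illustrative size.** Inputs from the plan are 55 per arm (7.3) and a two-sided 95% interval for the difference in rates (7.8). Assumed inputs are:

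- a common true response rate p, taken as 50% or 80% (the plan's two planning rates);
- a share m of true EndoRotor non-responders who end up classed as responders;
- no misreading in the control arm;
- an unadjusted, unpooled interval in place of the covariate-adjusted model.

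The apparent EndoRotor rate is p + (1 − p)·m. At p = 50% and m = 10% it is 0.50 + 0.50·0.10 = 55%. At p = 80% and m = 10% it is 0.80 + 0.20·0.10 = 82%. False superiority is the exact binomial probability, summed over all pairs of responder counts, that the lower 95% limit exceeds 0.

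| True rate, both arms | m | Apparent EndoRotor rate | False superiority |
|---|---|---|---|
| 50% | 0 | 50% | 2.4% |
| 50% | 10% | 55% | 7.4% |
| 50% | 20% | 60% | 18.4% |
| 80% | 0 | 80% | 2.7% |
| 80% | 10% | 82% | 4.9% |
| 80% | 20% | 84% | 8.4% |

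The normal approximation, Φ[(apparent difference)/SE − 1.96], gives 2.5%, 7.6% and 18.4% at 50%, and 2.5%, 4.5% and 7.9% at 80%. The pattern does not depend on the method.

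**The case against.** The strongest reply is that masking is already intended. The blinded-labelling sentence is followed by a caveat that ablation yields no tissue. That caveat makes most sense if the samples in question come from both arms, and section 5.8.1 does go on to discuss surveillance biopsies despite its heading. This is a fair reading. If it is the intended one, the remedy is to carry it into 5.8.2 and 5.8.3, where a site would look for the labelling and reading rules. It does not remove the gap.

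A reader might also infer that 5.8.1 and 5.8.2 contradict each other. They need not: on the narrow reading they govern different specimens.

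A reader might infer that the pathologist will know the arm. The documents do not say so, nor do they say what site labels or requisitions contain. A patient's identity on a jar is not the treatment arm. That the reader is local is itself an inference, from the term resident pathologist and from storage in the Department of Pathology.

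On size, three reservations stand. The misreading rate is assumed. All of the error is placed in EndoRotor's favour, although nothing in the plan gives the pathologist a stake in the result. And response needs two consecutive negative endoscopies, so one lenient reading does not by itself make a responder. For that reason m is defined per subject, not per reading, and the effect is shown at 80% as well as 50%.

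Finally, coded labels do not remove every cue. Section 5.5.3 describes indelible ink only for the EndoRotor arm, and the visual part of the endpoint remains open. Masking would be partial, but it would cover the main channel at low cost.

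**Conclusion.** The point holds as an absence of any secured masking for the endpoint histology. It does not establish a contradiction between sections or an unmasked read. Confidence is medium: the absence of a masking rule for these readings is clear from the text, but whether the arm would be visible, and whether that would move any reading, is not documented.

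If 10% to 20% of true EndoRotor non-responders were misclassified as responders, false superiority would be 7.4% to 18.4% at a 50% response rate and 4.9% to 8.4% at 80%, against about 2.5% without misreading. A reader might take 18.4% as the expected error rate; it is only the worst case among the scenarios shown. The change should be made because it is cheap and the trial is open-label, but the trial can run without it.

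**What to change.** In sections 5.8.2 and 5.8.3, state that:

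- surveillance biopsies from both arms go to Pathology under a study code with biopsy level and location, on labels and requisitions that do not disclose arm, device or study treatment received;
- the existing site pathologist reads them masked to arm;
- EndoRotor filter specimens are accessioned separately from the surveillance biopsies;
- site staff hold the code key, so that results can be re-linked to the patient and to the treated segment for the follow-up decisions already in the protocol.

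In section 5.8.1, say which specimens the blinded-labelling sentence covers.

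The cost is protocol wording, a coded requisition form, and a small labelling and re-linking effort at sites. No extra reader, visit or subject is needed, and no sample-size or power figure changes. The plan should acknowledge that masking is partial, because of the ink in EndoRotor-treated tissue and the open visual assessment by the endoscopist.

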5.8.3 Specimen Analysis

The resident pathologist shall be responsible for the review and interpretation of specimens collected.

6.0 Risks / Benefits Assessment

6.1 Risks to the Patient

The EndoRotor procedure poses no new risks to the patient than the commonly used mucosal resection techniques. As with all endoscopic resection and ablation devices, the most common risks are perforation and bleeding requiring intervention. Bleeding requiring intra-procedure intervention is not considered a serious adverse event and while it can occur it can be managed intra procedurally. Subjects may experience discomfort and pain post-procedure and after one to two days of the procedure. Other commonly known risks to a resection or ablation device include the following:

- Delayed bleeding occurring after the patient has been discharged requiring hospitalization and intervention
- Undiagnosed perforation resulting in free air in the mediastinum post-procedure

These are all common to established mucosal resection / ablation techniques and endoscopists are well practiced in handling these events. There are no additional risks that are particular to the EndoRotor® mechanical resection devices.

6.2 Mitigation Measures to Minimize Risk

All efforts will be made to minimize these potential risks by:

- Selection of qualified investigators and a qualified investigational center;
- Training the Investigator(s) on proper technique for EndoRotor® technique;
- Observation of procedures by the Interscope, Inc. and/or clinical personnel;
- Defining clear inclusion/exclusion criteria that ensure only appropriate subjects are enrolled and treated;
- Ensuring that the treatment and follow-up of subjects is consistent with current medical practice;
- Careful monitoring of adverse events, serious adverse events and device malfunctions by an Independent 3-Member Data Monitoring Committee and Interscope, Inc.;
- Adjudication of adverse events by an Independent 3-Member Data Monitoring Committee;
- Scheduled monitoring visits to the investigational site; and

- Regular communication with Investigator(s) and staff.

6.3 Potential Benefits to the Patient

The potential benefits of the EndoRotor® device are as follows:

- May be more comfortable (less pain) for the patient
- Complete removal of refractory BE lesions requiring no further treatments

7.0 STATISTICAL METHODS

7.1 General Principles

By-subject listings will be created for each CRF module. Summary tables for continuous variables will contain the following statistics: N, mean, median, standard deviation, minimum, maximum, and 95% confidence interval (CI) as appropriate. Summary tables for categorical variables will include N, percentage, and 95% CIs on the percentage. CIs for proportions will be calculated using the Clopper- Pearson exact method. Graphical techniques will be used when such methods are appropriate and informative. Tables will separate data by treatment arm.

Transformations of the data may be explored if warranted by the distribution of the data. Analyses resulting from transformations applied after the data are unmasked will be considered to be exploratory.

Unless otherwise specified, all analyses will be 2-sided at the 0.05 level of significance. All analyses will be performed using SAS® (Version 9.4) and graphs using R, version 3.3.1 or later, or using SAS®.

7.2 Analysis Populations

The safety analysis population is defined as all subjects who are treated with either EndoRotor® or continued ablative therapy. Subjects will be analyzed as treated.

The primary effectiveness analysis population is intent to treat (ITT), defined as all subjects who are randomized. Subjects will be analyzed as randomized. Missing primary and secondary endpoint data will be imputed.

A supportive effectiveness analysis population is Per Protocol (PP). This population is a subset of ITT and requires that subjects be treated with either EndoRotor® or continued ablative therapy, meet all inclusion/exclusion criteria, and are evaluated for effectiveness at no fewer than two post-treatment visits 3 months apart. Subjects will be analyzed as treated. Missing data will not be imputed.

